2.7.1.1 Adverse events of special interest / grouping of AEs

There are no AEs of special interest defined for this study.

2.7.2 Deaths

All deaths will be listed.

2.7.3 Laboratory data

Values and changes from pre-vaccination (where appropriate) in laboratory assessments will be summarized by cohort group and time point with descriptive statistics.

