## 8 Visit schedule and assessments

The below Assessment Schedules ([Table 8-1](#), [Table 8-2](#), [Table 8-3](#), [Table 8-4](#), [Table 8-5](#) and [Table 8-6](#)) list all assessments with an X when they are performed. All data obtained from these assessments must be supported in the participant's source documentation. The "X" in the table denotes the assessments to be recorded in the clinical database or received electronically from a vendor. The "S" in the table denotes the assessments that are only in the participant's source documentation and do not need to be recorded in the clinical database.

Participants should be seen for all visits/assessments as outlined in the assessment schedules or as close to the designated day/time as possible. The Investigator should promote compliance by instructing the participant to attend the study visits as scheduled and by stating that compliance is necessary for the participant's safety and the validity of the study. Missed or rescheduled visits should not lead to automatic discontinuation. The participant should be instructed to contact the Investigator if he/she is unable for any reason to attend a study visit as scheduled or if he/she is unable for any reason to take the study treatment as prescribed.

Participants who prematurely discontinue the study should be scheduled for the End of Study (EOS) visit within 7 days. At this final visit, all the assessments mentioned under EOS visit should be performed, all dispensed investigational product should be reconciled, and the

adverse event and concomitant medications recorded on the CRF. Participants that prematurely discontinue should also have a remote follow-up safety visit performed 30 days after the EOS visit.

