### **Clinical laboratory evaluations**

All laboratory data will be listed by cohort, participant, and visit/time and if normal ranges are available abnormalities will be flagged. Summary statistics will be provided by cohort. Shift tables using the low/normal/high/ (low and high) classification will be used to compare baseline to the worst on-treatment value.

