2.4.1.1 Visit windows

Visit windows will be used for data that are summarized by visit; they are based on the study evaluation schedule and comprise a set of days around the nominal visit day. When visit windows are used, all visits, including unscheduled visits, will be re-aligned (i.e., they will be mapped into one of the visit windows). In the case of major deviations from the visit schedule, or due to unscheduled visits, several assessments for a participant may fall in a particular visit window (either scheduled or unscheduled). Approaches for handling multiple assessments in a visit window are outlined below.

The following steps are used to determine the cut-offs for visit windows:

- The visit window associated with the previous assessment ends prior to the middle point; the visit window associated with the latter assessment begins after the middle point. In case the middle point is an exact study day, it will belong to the previous assessment.
- The visit window of the first post-vaccination assessment starts the day after the second dose of the COVID-19 vaccine for Cohorts 1 – 5, and the day after the COVID-19 vaccine booster for Cohort 6, unless otherwise specified.

Tables 2 – 10 provide visit windows for applicable parameters.

Table 2**Cohort 1 visit windows for SARS-CoV-2 qualitative antibody / CD19+ B cells / T cell**

Analysis visit	Nominal time point	Scheduled visit day (target study day)	Visit window (study days)
Pfizer vaccine:			
Pre-vaccination	Day 1	1	≤1
14 days post-vaccination	Day 36	36	(vaccine day + 1) to 64
70 days post-vaccination	Day 92	92	65 to 147
180 days post-vaccination	Day 202	202	148 to 247
270 days post-vaccination	Day 292	292	248 to 337
360 days post-vaccination	Day 382	382	≥338
Moderna vaccine:			
Pre-vaccination	Day 1	1	≤1
14 days post-vaccination	Day 43	43	(vaccine day + 1) to 71
70 days post-vaccination	Day 99	99	72 to 154
180 days post-vaccination	Day 209	209	155 to 254
270 days post-vaccination	Day 299	299	255 to 344
360 days post-vaccination	Day 389	389	≥345

Note:

- Pre-vaccination and study day are derived as outlined in [Section 2.1.1](#).
- Vaccine day is the study day of the second dose of the COVID-19 vaccine.
- Assessments performed between the first and second doses of the COVID-19 vaccine are not assigned an analysis visit.

Table 3**Cohort 1 visit windows for serum immunoglobulin (IgG, IgM)**

Analysis visit	Nominal time point	Scheduled visit day (target study day)	Visit window (study days)

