Pfizer vaccine:			
Pre-vaccination	Day 1	1	≤1
14 days post-vaccination	Day 36	36	(vaccine day + 1) to 64
70 days post-vaccination	Day 92	92	65 to 147
180 days post-vaccination	Day 202	202	148 to 292
360 days post-vaccination	Day 382	382	≥293
Moderna vaccine:			
Pre-vaccination	Day 1	1	≤1
14 days post-vaccination	Day 43	43	(vaccine day + 1) to 71
70 days post-vaccination	Day 99	99	72 to 154
180 days post-vaccination	Day 209	209	155 to 299
360 days post-vaccination	Day 389	389	≥300

Note:

- Pre-vaccination and study day are derived as outlined in [Section 2.1.1](#).
- Vaccine day is the study day of the second dose of the COVID-19 vaccine.
- Assessments performed between the first and second doses of the COVID-19 vaccine are not assigned an analysis visit.

[figure not shown]

Table 5**Cohorts 2 and 3 visit windows for SARS-CoV-2 qualitative antibody / CD19+ B cells (Cohort 2 only) / T cell**

Analysis visit	Nominal time point	Scheduled visit day (target study day)	Visit window (study days)
Pfizer vaccine:			
Pre-vaccination	Day 1	1	≤1
14 days post-vaccination	Day 36	36	(vaccine day + 1) to 119
180 days post-vaccination	Day 202	202	120 to 247
270 days post-vaccination	Day 292	292	248 to 337
360 days post-vaccination	Day 382	382	≥338
Moderna vaccine:			
Pre-vaccination	Day 1	1	≤1
14 days post-vaccination	Day 43	43	(vaccine day + 1) to 126
180 days post-vaccination	Day 209	209	127 to 254
270 days post-vaccination	Day 299	299	255 to 344
360 days post-vaccination	Day 389	389	≥345

Note:

- Pre-vaccination and study day are derived as outlined in [Section 2.1.1](#).
- Vaccine day is the study day of the second dose of the COVID-19 vaccine.
- Assessments performed between the first and second doses of the COVID-19 vaccine are not assigned an analysis visit.

Table 6**Cohorts 2 and 3 visit windows for serum immunoglobulin (IgG, IgM)**

Analysis visit	Nominal time point	Scheduled visit day (target study day)	Visit window (study days)
Pfizer vaccine:			
Pre-vaccination	Day 1	1	≤1
180 days post-vaccination	Day 202	202	(vaccine day + 1) to 292
360 days post-vaccination	Day 382	382	≥293
Moderna vaccine:			
Pre-vaccination	Day 1	1	≤1
180 days post-vaccination	Day 209	209	(vaccine day + 1) to 299
360 days post-vaccination	Day 389	389	≥300

Note:

- Pre-vaccination and study day are derived as outlined in [Section 2.1.1](#).
- Vaccine day is the study day of the second dose of the COVID-19 vaccine.

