- Assessments performed between the first and second doses of the COVID-19 vaccine are not assigned an analysis visit.

Table 8**Cohorts 4, 5 and 6 visit windows for SARS-CoV-2 qualitative antibody / CD19+ B cells (Cohorts 4 and 6 only) / T cell**

Analysis visit	Nominal time point	Scheduled visit day (target study day)	Visit window (study days)
Pfizer vaccine:			
14 days post-vaccination	Day 1	1	(vaccine day + 1) to 1
180 days post-vaccination	Day 202	202	2 to 247
270 days post-vaccination	Day 292	292	248 to 337
360 days post-vaccination	Day 382	382	≥338
Moderna vaccine:			
14 days post-vaccination	Day 1	1	(vaccine day + 1) to 1
180 days post-vaccination	Day 209	209	2 to 254
270 days post-vaccination	Day 299	299	255 to 344
360 days post-vaccination	Day 389	389	≥345

Note:

[figure not shown]
- Study day is derived as outlined in [Section 2.1.1](#).
- Vaccine day is the study day of the second dose of the COVID-19 vaccine for Cohorts 4 and 5, and the study day of the COVID-19 vaccine booster for Cohort 6.

Table 9 **Cohorts 4, 5 and 6 visit windows for serum immunoglobulin (IgG, IgM)**

Analysis visit	Nominal time point	Scheduled visit day (target study day)	Visit window (study days)
Pfizer vaccine:			
14 days post-vaccination	Day 1	1	(vaccine day + 1) to 1
180 days post-vaccination	Day 202	202	2 to 292
360 days post-vaccination	Day 382	382	≥293
Moderna vaccine:			
14 days post-vaccination	Day 1	1	(vaccine day + 1) to 1
180 days post-vaccination	Day 209	209	2 to 299
360 days post-vaccination	Day 389	389	≥300

Note:

- Study day is derived as outlined in [Section 2.1.1](#).
- Vaccine day is the study day of the second dose of the COVID-19 vaccine for Cohorts 4 and 5, and the study day of the COVID-19 vaccine booster for Cohort 6.

Multiple assessments

When there are multiple assessments in a particular visit window, the rules outlined below are applied to select one value “representing” the participant in summary statistics for that visit window. All assessments will be displayed in listings.

- **Pre-vaccination (only applicable to Cohorts 1, 2 and 3):** Pre-vaccination is derived as outlined in [Section 2.1.1](#). In situations where the same assessment is performed more than once on Study Day 1 the repeated assessment will be used.
- **Post-vaccination:** For post-vaccination visit windows, the following rules apply (unless otherwise specified):

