 - For *continuous variables*, the assessment with the study day that is closest to the target study day is selected. If two assessments are equidistant from the target study

day, the earlier assessment is selected (if one of the two equidistant assessments is an unscheduled assessment, it should be excluded from consideration).

- For *categorical variables*, the assessment with the worst result is selected.

If categorical variables are based on continuous variables, the analysis visit will be assigned to the continuous variable, and this analysis visit will be used for the derived categorical variable.

In situations where the same assessment is performed more than once on the same date the repeated assessment will be used.

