2.13 Interim analysis

For the purpose of early dissemination of results, an IA will be performed once Cohorts 2 and 4 in combination have ≥ 10 participants enrolled that have had their serum drawn ≥ 14 days after full course (2 doses) vaccination.

A second IA will be performed once Cohort 6 has ≥ 10 participants.

The third IA will be performed once Cohorts 2 – 5 have full enrollment with blood drawn ≥ 14 days after full course (2 doses) vaccination.

The following variables (including but not limited to) will be summarized for each IA mentioned above:

- Disposition
- Demographics

- Baseline characteristics
- Immune response-related variables
- AEs, SAEs and AEs leading to study discontinuation
- Deaths

Since there will be no hypothesis testing involved, statistical adjustment for the IA will not be made at the stage of final analyses.

3 Sample size calculation

The sample size of 20 participants per cohort is selected based on budget and need for early availability of results. This sample size of 20 participants will provide estimates of proportion of responders with margin of error (half-width of a 95% CI) of 20.1%, 19% and 17.5% corresponding to response rates of 70%, 75% and 80%, respectively. Adjusting for 10% drop-out, 22 participants will be enrolled in Cohort 1. In combination, 22 participants will be enrolled in Cohorts 2 and 4. In combination, 22 participants will be enrolled in Cohorts 3 and 5. In Cohort 6, 22 participants will be enrolled.

4 Change to protocol specified analyses

There are no changes to protocol specified analyses.

5 Appendix

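### SAP 2.7.3 leaves out the protocol's baseline-to-worst laboratory shift table without declaring it, and the by-visit summary that remains can miss a new low immunoglobulin at an early End of Study visit

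*SAP*

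**What the plan says.** The protocol's paragraph on clinical laboratory evaluations (under 12.5.1) plans a listing with abnormalities flagged, summary statistics by cohort, and this: "Shift tables using the low/normal/high/ (low and high) classification will be used to compare baseline to the worst on-treatment value".

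SAP 2.7.3 keeps the summary statistics: "Values and changes from pre-vaccination (where appropriate) in laboratory assessments will be summarized by cohort group and time point with descriptive statistics". No laboratory shift table or worst-value table appears elsewhere in the SAP text supplied. SAP section 4 reads: "There are no changes to protocol specified analyses".

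Three further rules decide what the by-visit summary contains:

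- SAP 2.4.1.1 assigns results to analysis visits by study day: "all visits, including unscheduled visits, will be re-aligned".
- Where a window holds several values of a continuous variable, "the assessment with the study day that is closest to the target study day is selected"; the other values go to listings.
- Protocol section 8 provides a last visit for those who leave early: "Participants who prematurely discontinue the study should be scheduled for the End of Study (EOS) visit within 7 days". All End of Study assessments are to be done then, and the schedules in Tables 8-1 and 8-3 to 8-6 show serum immunoglobulin among them.

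**The concern.** A safety table in the supplied protocol is missing from the SAP, and the section meant for such departures does not mention it. A worst-value table does something the by-visit summary cannot. It uses each participant's lowest result whenever it was drawn, and it counts participants who move from normal to low. The statistics in SAP 2.1 (n, mean, standard deviation, quartiles, extremes) give no such count.

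Immunoglobulins are the laboratory values where this matters most. Protocol 4.5 names decreased IgM as an adverse reaction to ofatumumab, and the protocol sets IgG limits for entry, for stopping treatment and for withdrawal. At stake is a complete summary of low values, including those found as a participant leaves. The immune-response analyses are not involved.

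**Working it through.** **Inputs.** Serum immunoglobulin target days and windows are in SAP Tables 3 (Cohort 1), 6 (Cohorts 2 and 3) and 9 (Cohorts 4 to 6). The selection and cut-off rules are in SAP 2.4.1.1. Draw days are in the assessment schedules in protocol section 8.

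**Step 1: reproduce the SAP's cut-offs.** The rule is the midpoint between neighbouring target days, with an exact midpoint going to the earlier visit.

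- Cohort 1, Pfizer: (36 + 92)/2 = 64; (92 + 202)/2 = 147; (202 + 382)/2 = 292.
- Cohort 1, Moderna: (43 + 99)/2 = 71; (99 + 209)/2 = 154; (209 + 389)/2 = 299.
- Cohorts 2 to 6: 292 (Pfizer) and 299 (Moderna).

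All match the tables.

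**Step 2: one example.** A Pfizer participant has a normal IgG on Day 202, then leaves, and has a low IgG at an End of Study visit on Day 240. Both days lie in the window ending on Day 292. The distances to the target are 0 and 38 days, so Day 202 is selected. Day 240 is not in the 360-day window, which starts on Day 293. The low value is in no summary row. The worst-result rule for categorical variables does not rescue it, because a category derived from a continuous variable takes that variable's analysis visit.

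**Step 3: all days on which this happens.** With earlier scheduled draws on target, an early End of Study value is never selected on these days:

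| Cohorts | Pfizer | Moderna | Days |
|---|---|---|---|
| 2 to 6 | 203-292 | 210-299 | 90 |
| 1 | 37-64, 93-147, 203-292 | 44-71, 100-154, 210-299 | 28 + 55 + 90 = 173 |

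If the Day 202 draw is three days early, the last Pfizer range is Days 205-292 (88 days). If it is three days late, the range is Days 206-292 (87 days).

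**Step 4: share of possible early End of Study days (Pfizer).** The days run from the start of the first post-vaccination window to the day before the scheduled End of Study visit.

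- Cohorts 4 to 6, Days 2-381: 90/380 = 24%.
- Cohorts 2 and 3, second dose on Day 22, Days 23-381: 90/359 = 25%.
- Cohort 1, Days 23-381: 173/359 = 48%.

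These are shares of calendar days, not probabilities. The documents give no distribution of drop-out times and no rate of low values.

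**Step 5: what the shift table would do.** It would use the Day 240 value, provided an End of Study draw counts as on-treatment. The protocol does not define that period in days, so this is an assumption.

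**The case against.** The strongest reply is that the IgG case on which this trial acts is already visible. An IgG below 400 mg/dl at an on-target scheduled draw is the selected value, and the row minimum shows it. The withdrawal is listed with its reason (SAP 2.3.1). Clinically significant abnormalities may also be reported as adverse events (protocol 8.4.1), and every value is listed (SAP 2.1). This stands. The unsummarised case is narrower: a new low value at an early End of Study visit after a normal scheduled draw in the same window. An early End of Study value that is alone in its window is summarised.

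The restored table would also have limits. Cohorts 2, 4 and 6 enter already on ofatumumab, so their baseline is not a pre-drug value. Screening immunoglobulins taken from recent local results stay in source documents, so some participants have no baseline in the database. Both limits are real, and both can be labelled.

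Four stronger readings are tempting, and the documents do not support them.

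- **That SAP section 4 is plainly false.** The SAP says it implements Section 12 of protocol version 01, and the supplied protocol is a later amendment. The stated rationale of Amendment 2 mentions no new laboratory analysis, but version 01 cannot be checked.
- **That half of all early End of Study values are lost in every cohort.** Between the Day 202 and Day 382 draws it is 90 of 179 days (50%), but that counts only participants who have already reached Day 202.
- **That up to 8 of 88 participants are affected** (22 - 20 = 2 per group, times 4). The 10% drop-out allowance belongs to the primary endpoint, which is read at Visit 4 or Visit 2. It says nothing about later drop-out or about low values.
- **That the shift table would count IgG below 400 mg/dl.** It classifies by low, normal and high, not by the trial's 400 mg/dl limit.

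Participants withdrawn for low IgG are missing from later rows, but that is true of any by-visit summary and is not caused by this omission.

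**Conclusion.** The point holds as a minor one. Against the supplied protocol, a specified safety table is absent from the SAP and its absence is not declared. The by-visit summary does not fully replace it, because the SAP's own windows leave a defined set of early End of Study days on which a new low IgG or IgM reaches no summary row.

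The size in days is exact given on-target draws: 90 days in Cohorts 2 to 6 and 173 in Cohort 1. The number of participants is unknown. The conclusion rests on two conditions: that the supplied protocol is the right reference, and that an End of Study draw counts as on-treatment. The values remain in listings, and no immune-response endpoint is affected.

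**What to change.** In SAP 2.7.3, restore the shift table by cohort group, using the laboratory's low, normal and high limits, with these rules:

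- **Values:** all scheduled, unscheduled and End of Study results after baseline. State that the closest-to-target selection does not apply to this table.
- **Baseline:** the pre-vaccination value in Cohorts 1 to 3 and the screening value in Cohorts 4 to 6, labelled in the latter as an on-treatment reference. Note that Cohort 2 also enters on ofatumumab.
- **Cohort 1:** include the Visit 4 draw (Day 36 or 43), flagged as taken before the first ofatumumab dose. Protocol 6.3.2 places that dose after the visit's assessments. Starting the period at the first dose would leave this draw as neither baseline nor follow-up.
- **Missing baseline:** print the number of participants with no baseline value in the database.

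If the table is not restored, declare and justify its removal in SAP section 4.

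The cost is SAP wording and one extra table, with no new samples or visits. The downside is that some participants cannot be classified because their screening result is only in source documents. A separate count of participants at the 400 mg/dl limit is optional. The difference between protocol 8.5.2 and 9.1.1 (below 400) and 9.1.2 (400 or below) is a separate matter for the protocol.

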2.7.4 Other safety data

2.7.4.1 MS relapse

The number and percentage of participants with 0, 1, 2 or ≥ 3 confirmed relapses during the study will be presented by cohort group. In addition, the number and percentage of participants with at least 1 confirmed relapse during the study will be presented by cohort group.

2.8 Pharmacokinetic endpoints

There are no pharmacokinetic (PK) endpoints defined for this study.

2.9 PD and PK/PD analyses

[figure not shown]
There are no pharmacodynamic (PD) or PK/PD analyses planned for this study.

[figure not shown]
2.10 Patient-reported outcomes

There are no patient-reported outcome endpoints defined for this study.

2.11 Biomarkers

There are no biomarker endpoints defined for this study.

2.13 Interim analysis

For the purpose of early dissemination of results, an IA will be performed once Cohorts 2 and 4 in combination have ≥ 10 participants enrolled that have had their serum drawn ≥ 14 days after full course (2 doses) vaccination.

A second IA will be performed once Cohort 6 has ≥ 10 participants.

The third IA will be performed once Cohorts 2 – 5 have full enrollment with blood drawn ≥ 14 days after full course (2 doses) vaccination.

The following variables (including but not limited to) will be summarized for each IA mentioned above:

- Disposition
- Demographics

- Baseline characteristics
- Immune response-related variables
- AEs, SAEs and AEs leading to study discontinuation
- Deaths

Since there will be no hypothesis testing involved, statistical adjustment for the IA will not be made at the stage of final analyses.

3 Sample size calculation

The sample size of 20 participants per cohort is selected based on budget and need for early availability of results. This sample size of 20 participants will provide estimates of proportion of responders with margin of error (half-width of a 95% CI) of 20.1%, 19% and 17.5% corresponding to response rates of 70%, 75% and 80%, respectively. Adjusting for 10% drop-out, 22 participants will be enrolled in Cohort 1. In combination, 22 participants will be enrolled in Cohorts 2 and 4. In combination, 22 participants will be enrolled in Cohorts 3 and 5. In Cohort 6, 22 participants will be enrolled.

4 Change to protocol specified analyses

There are no changes to protocol specified analyses.

5 Appendix

5.1 Imputation rules

5.1.1 Study drug

There will be no imputation rules for study drug detailed for this study.

5.1.2 AE date imputation

The following algorithm will be used to estimate AE start dates for which only partial information is known. Note that “index date” refers to the date of Visit 1 (Screening).

Missing day and month:

- If the year is the same as the year of the index date, then the day and month of the index date will be assigned to the missing fields.
- If the year is prior to the year of the index date, then December 31 will be assigned to the missing fields.
- If the year is after the year of the index date, then January 1 will be assigned to the missing fields.

Missing month only:

- Treat day as missing and replace both month and day according to the above procedure.

Missing day only:

- If the month and year are the same as the year and month of the index date, then the index date will be assigned to the missing day.
- If the month and year are before the year and month of the index date, then the last day of the month will be assigned to the missing day.
- If the month and year are after the year and month of the index date, then the first day of the month will be assigned to the missing day.

If the imputed start date result is after the stop date (and the stop date is complete), the imputed start date will be reset to the stop date.

The following algorithm will be used to estimate AE stop dates for which only partial information is known.

Missing year:

- Date left missing.

Missing month:

- Impute ‘December’.

Missing day:

- Impute ‘last date of that month’.

